1. SYNOPSIS

Study Title	Monitoring of Cervical lesions at Colposcopy using a novel non-invasive technique for monitoring of CIN2 lesions (a pilot/ feasibility study)			
Internal ref. no.	R&D			
Study Design	The is a single-centre, non-randomised, cohort interventional & lab based study			
Study Participants	Women with abnormal cytology attending the colposcopy clinic that have single quadrant disease that is histologically CIN2. The women will be identified from the larger Cervical Cell Lift study (17/SC/0203) or from the pre-existing standard of care conservative management pathway.			
Planned Sample Size	10			
Follow-up duration	From 6 months to 1 year (3 monthly intervals)			
Planned Study Period	12 to 18 months			
Primary Objective	To non-invasively monitor women with CIN2 using a novel non-invasive approach in order to identify biomarker patterns that are consistent with lesion regression/ progression			
Secondary Objectives	None			
Primary Endpoint	As this is a feasibility study, the outcome is considered to be the ability to identify biomarker patterns consistent with lesion regression/ progression			
Secondary Endpoints	-			
Intervention (s)	 If enrolled to the study after CIN2 diagnosis: Primary visit for Colposcopy – CIN2 identified, acetowhite photograph and Patch taken followed by biopsy 3-month visit for Colposcopy – Patch, acetowhite photograph taken and colposcopy done to ensure no change in lesion and comparison with previous photograph of acetowhite change 6-month visit for Colposcopy - Patch, acetowhite photograph taken and colposcopy done to ensure no change in lesion and comparison with previous photograph of acetowhite change 9-month visit for Colposcopy - Patch, acetowhite photograph taken and colposcopy done to ensure no change in lesion and comparison with previous photograph of acetowhite change 9-month visit for Colposcopy - Patch, acetowhite photograph taken and colposcopy done to ensure no change in lesion and comparison with previous photograph of acetowhite change 1-year visit for Colposcopy – Patch, acetowhite photograph taken and either further biopsy or excisional treatment as per colposcopist impression If enrolled to the study from the pre-existing clinical pathway, participants will start the study at either the 3 month visit (-/+ 2 week) or the 6 month routine clinical visit (-/+ 2 week) following CIN2 diagnosis. 			

BACKGROUND AND RATIONALE

Outline the scientific justification for the research. Give an outline of the background to the study, with references to literature and other relevant research.

Give an outline of the main research questions. Give a brief outline of the intervention (if applicable) and summary of findings from previous studies (if relevant) that potentially have clinical significance.

Provide summary of the known and potential risks and benefits of any of the study procedures (where applicable)

Describe the population to be studied.

The purpose of this study is to non-invasively monitor women with histologically identified CIN2 lesions. CIN2 lesions are pre-cancer lesions that are caused by HPV. These lesions can in a small subset of patients progress onto CIN3 lesions and eventually cervical cancer. The duration of this progression is usually over 1 year (for CIN3 and longer for cervical cancer) and indeed the majority of these lesions would actually regress (especially in <30 year olds) due to immune control and HPV clearance(1–5). This understanding of CIN2 progression has led to changes in the management of CIN2 lesions, where in the past all such patients would be offered excisional treatment, we have now moved towards adopting a watch and wait policy (with usually 6 monthly colposcopy follow-ups)(6).

Our current ongoing study (17/SC/0203 - Collection of Cervical Cells at Colposcopy using a novel technique for analysis of high risk vs. low risk lesions) has demonstrated that using our non-invasive approach we can identify high-grade (CIN2+) and low-grade (CIN1/ negative) lesions using a biomarker panel. This approach has yielded numerous advantages and in particular the ability to identify lesions in their entirety together with their location on the cervix (Fig 1). This approach is now being validated on a larger cohort of patients and is being assessed to become the test of choice for HPV triage. The biomarkers we have settled on are p16/MCM (markers of CIN2+) and E4 (marker of CIN1). These markers have been independently verified by our group and others as being sensitive markers to clinically relevant disease and indeed this panel of markers, by improving the objectiveness of diagnosis, improves the sensitivity of subjective approaches such as histology/ cytology to CIN2+ lesions(7).

Fig 1. Patch stained with MCM demonstrating a CIN3 lesion in its entirety. Inset demonstrates lesion magnified

Our current approach involves the use of a disk of nitrocellulose to lift the cells from the surface of the cervix. Prior to the disc being applied a photograph of the cervix is taken and once the disc is removed (application time of <15 seconds) a photograph of the cervix treated with acetic acid is taken (as per routine colposcopy practice). The disc is then probed in the lab with our marker panel and then analysed for lesions. In our pilot study of 50 patients we have demonstrated a sensitivity of 88% to CIN2+ lesions with a corresponding positive predictive value of 84% (in this enriched population). These results are better than cytology triage of HPV positive women and in terms of detecting clinically relevant disease superior p16 as well (Fig 2). We are now expanding this approach to a larger cohort over multiple sites.

Concurrent to this we would now like to use this approach to monitor disease in a subset of patients (n=10) who have CIN2 lesions on histology. The use of a non-invasive sampling process enables diagnosis of patients without the need for a biopsy, the ability to monitor patients in the community and finally, due to the low positive-predictive value (14%) of HPV screening, the ability to triage patients with confidence in the community thus improving the overall patient diagnostic pathway. Moreover, the treatment for CIN2 lesions historically has been excisional in nature (Loop excisions), which we now know increases the risk of pre-term labour. This is significant as the majority of women requiring treatment are of child-bearing age, thus the ability to offer these women a non-invasive molecular monitoring method, in an era of personalized treatment, is warranted.

The study will involve monitoring patients with our non-invasive technique in conjunction with colposcopy (Fig 3) to assess the feasibility of this method. The main risk to any patient is the risk of progression to CIN3 and worse cancer. However, as the majority of CIN2 patients across the UK are now offered conservative management and as many recent papers have demonstrated lesion regression in >50% of CIN2 cases this risk (over the duration of the study) is extremely low(1–6). Moreover, in order to further minimize this risk, we will follow-up these patients more intensively than the norm (usually conservative management of CIN2 involves 6-month follow-up colposcopy) with 3 monthly colposcopy visits for up to 1 year with the same named colposcopist (to reduce any inter-observer variability) where possible. If a different colposcopist is used, we will aim to mitigate

any increased variability by using and comparing colposcopic photographs taken during each colposcopy visit. This will allow us to ensure that variations in diagnosis are kept to a minimum.

Finally, as we are using biomarkers to identify lesions on the patch, any marker pattern that is suggestive of higher-grade disease will result in the patient having a colposcopic visit together with adequate counselling and biopsies/ treatment as required. We feel that this approach enables us to minimize the already low risk of progression even further thus allowing women to give informed consent in an ethical manner. There are no operceivable risks involved.

Fig 3. Study scheme demonstrating entire patient pathway including patient withdrawal points. Colposcopic photographs will be taken during each colposcopy visit and all histology will be reviewed/compared by histopathologists. A) Pathway for patients who recruited after diagnosis with CIN2, B)) Pathway for patients who recruited from the pre-existing clinical pathway either at 3 month visit (-/+ 2 week) or at the 6 month routine clinical visit (-/+ 2 week).

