3.1 Primary Objective

The aim of the project is to assess the feasibility of this non-invasive sampling method to monitor CIN2 lesions in order to identify biomarker patterns that are consistent with lesion progression/ regression.

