4.2 Primary and Secondary Endpoints/Outcome Measures

As this is a feasibility study, the primary measure is that of demonstrating initial utility of this approach to non-invasively monitor women with CIN2 lesions and demonstrate biomarker patterns that are consistent with lesion regression or progression.

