4.5 Definition of End of Study

The recruitment of new participants will stop when 10 evaluable patients have been recruited to the study or by the end of 2022, whichever is sooner. Evaluability is determined by having at least 3 full datasets (3 different time points). The study will end when the last patient has completed her last follow-up visit. Any participants recruited after the 10th evaluable participant who are still active in the study will be followed -up and included in the final analysis. The total number of participants recruited to the study may therefore be more than 10. All data capture will stop at the end of 2022, regardless of whether the full set of 10 evaluable participants has been accrued.

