5. STATISITICS

6.1 The Number of Participants

We have identified 10 patients as a suitable number for this study (as it is a pilot). This will enable a robust analysis of the merits of non-invasive sampling and CIN2 progression. There is a risk of patients dropping out/ withdrawing consent during the study time period. Thus, we will only count patients that have completed the full study duration.

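### The protocol sets out to assess feasibility of repeat sampling but measures no feasibility quantity, and counting only completers makes retention uninformative

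*Protocol*

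**What the plan says.** **Aim.** Section 3.1 of the protocol: "The aim of the project is to assess the feasibility of this non-invasive sampling method to monitor CIN2 lesions". The same sentence goes on to give the purpose, which is to find marker patterns that go with progression or regression. The Ethics section justifies the extra visits on two grounds: learning about marker patterns, and assessing whether sampling these women non-invasively is feasible.

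**Endpoint.** In the synopsis, "the outcome is considered to be the ability to identify biomarker patterns consistent with lesion regression/ progression". In section 4.2, "the primary measure is that of demonstrating initial utility of this approach to non-invasively monitor women with CIN2 lesions", together with showing such patterns. There are no secondary objectives or endpoints.

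**Analysis.** Section 6.2 looks for a correlation between marker pattern and final histology or colposcopy outcome. It expects lesions with high E4 to regress, and the reverse.

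**Who is counted.** Section 6.1 acknowledges dropout and concludes: "Thus, we will only count patients that have completed the full study duration". Section 4.5 says "The recruitment of new participants will stop when 10 evaluable patients have been recruited", with the end of 2022 as an alternative stop, and then "Evaluability is determined by having at least 3 full datasets (3 different time points". It allows more than 10 women to be recruited and keeps later recruits who are still active in the final analysis.

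**The concern.** A study of whether repeat patch sampling is workable should report how often it worked: how many scheduled patches could be read, and how many women gave enough samples to be followed. None of the endpoint or analysis text asks for either number. Pattern identification answers a related but different question, namely whether the markers track the lesion once the samples exist.

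Section 6.1 adds to this. Women who drop out are part of the evidence on feasibility, and under that rule they are not counted. A report that follows it literally could present 10 women, all with complete follow-up, without showing how many were enrolled to get there. Anyone planning a larger monitoring study would then lack the two rates needed to plan it.

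**Working it through.** **1. Plan's own figure.** The sample size of 10 is stated as suitable for a pilot. No precision target, dropout rate or hypothesis test is given, so there is nothing to reproduce.

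**2. Aim against measurement.**

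| Place | Content | Feasibility quantity? |
|---|---|---|
| 3.1 | Feasibility of the method, for the purpose of finding patterns | Named as the aim |
| Ethics | Patterns, and also feasibility of sampling | Named separately |
| Synopsis endpoint | Ability to identify patterns | None |
| 4.2 | Initial utility, and patterns | None |
| 6.2 | Correlation of pattern with outcome | None |

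**3. The two counting rules.** The Interventions section gives one baseline and up to four further examinations, so five for a woman entering at diagnosis. Entry at month 3 leaves four (months 3, 6, 9, 12) and entry at month 6 leaves three. The share of visits needed to be evaluable under section 4.5 is therefore:

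- entry at diagnosis: 3/5 = 60%
- entry at month 3: 3/4 = 75%
- entry at month 6: 3/3 = 100%

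The rules can disagree about the same woman. One who enters at diagnosis, gives full datasets at baseline and months 3 and 6, and then withdraws is evaluable under 4.5 but not counted under 6.1. One who attends to month 12 but yields only two full datasets is counted under 6.1 but not evaluable under 4.5.

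**4. Effect of the denominator.** Under 6.1, with c completers, retention among those counted is c/c = 100% for any c and any dropout. With all enrolled women as denominator it is x/n, where x is the number evaluable and n the number enrolled. The exact (Clopper-Pearson) 95% limits are the 0.025 quantile of Beta(x, n − x + 1) and the 0.975 quantile of Beta(x + 1, n − x). When x = n the lower limit is 0.025^(1/n), so for 10/10 it is 0.025^(0.1) = 0.69, with an upper limit of 1.

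The values of n below are assumptions. The last column supposes that the 10 evaluable women are also completers.

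| Enrolled | Loss implied | 10 evaluable / enrolled | Exact 95% CI | Completers only |
|---|---|---|---|---|
| 12 | 2/12 = 17% | 83% | 52-98% | 10/10 (69-100%) |
| 14 | 4/14 = 29% | 71% | 42-92% | 10/10 (69-100%) |
| 20 | 10/20 = 50% | 50% | 27-73% | 10/10 (69-100%) |

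The last column is the same in every row, so it carries no information about retention.

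**The case against.** The strongest reply is that feasibility here means whether patch markers can follow a lesion. The synopsis objective and synopsis endpoint match almost word for word, and the aim in 3.1 includes finding patterns. This stands in part: the endpoint does address part of the aim, and it would be wrong to say that it misses the objective altogether. But the Ethics section lists feasibility of sampling as a separate gain, and nothing measures it.

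A second reply is that section 6.1 sits under the number of participants and may only say who counts towards 10, not who is analysed. That reading is possible. It does not remove the conflict with 4.5, which also defines who counts towards 10.

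A reader might go further and infer that the study cannot fail or can only conclude that the method is feasible. The documents do not support that:

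- Section 6.2 states an expected direction, which the data could contradict.
- Section 4.5 stops data capture at the end of 2022 even with fewer than 10 evaluable women. For illustration, with 12 enrolled and independent losses at rate d, the chance of at least 10 evaluable is the sum over k = 10 to 12 of C(12,k)(1 − d)^k d^(12−k). This is 89%, 56% and 25% for assumed d of 10%, 20% and 30%, so a shortfall is a real possibility.
- Under 4.5 a woman may lack a full dataset at two of five visits and still be evaluable.
- Nothing says that unreadable stains are removed from a woman's record, so patch adequacy is not fixed at 100%.

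A reader might also infer that the completer rule drops women whose lesions progress, because the Background says a higher-grade marker pattern leads to colposcopy with biopsy or treatment as needed. The text does not say whether such a woman is treated as not having completed, so this is not established.

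**Conclusion.** The point holds in a limited form. The protocol names feasibility of the sampling method as an aim, yet specifies no feasibility quantity. Section 6.1 makes retention among counted women 100% by definition and conflicts with the evaluability rule in 4.5. Because the protocol itself fixes the endpoint and both counting rules, this is not detail left to an analysis plan.

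The size is unknown, since no dropout rate is given. At the assumed enrolments of 12 to 20, the proportion evaluable would run from 83% down to 50%, against an unchanging 100% under completer counting. These are hypothetical observed proportions, not estimates of a true rate. The intervals treat enrolment as fixed, although recruitment is tied to reaching 10 evaluable women, so they show the order of the uncertainty. Even 10 out of 10 enrolled would leave a lower limit of 69%.

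The finding does not require the marker-pattern endpoint to be demoted or replaced. That would be a debatable choice, and the gap can be closed without it.

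**What to change.** - **Sections 4.5 and 6.1:** use one rule, at least three full datasets, for counting towards 10; say what a full dataset contains; and state that all enrolled women stay in the report.
- **Synopsis, 4.2 and 6.2:** keep the marker-pattern endpoint and add, alongside it, (a) women reaching at least three full datasets over all enrolled women, with an exact 95% CI, and (b) patches with a readable E4/p16/MCM stain over scheduled patches, with an interval that allows for several visits per woman.

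The cost is a few sentences and a simple log of patch readability, which the protocol does not say is already kept. No extra visit or sample is needed. The one drawback for the sponsor is that the headline rate may look less favourable than a completers-only count.

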3.4 Study Procedures

- 1. Written informed consent will be given prior to the patient's initial colposcopy
- 2. During the colposcopy examination, a digital image of the cervix will be taken according to standard practice.
- 3. A filter disk of nitrocellulose (of up to 50mm diameter and marked to indicate the 12 O'clock position) will then be gently pressed onto the surface of the cervix for 10 to 15 seconds prior to it being peeled off and removed for storage. The filter with adherent exfoliated cells will then be fixed (in acetone/methanol, ethanol, or 5% formaldehyde) prior to analysis at the level of cytology or immunostaining or DNA/ RNA analysis as part of the research collaboration between the University of Cambridge and Addenbrookes Hospital.
- 4. The remainder of the colposcopy examination will then follow its standard course, with identification of single quadrant disease and impression of CIN2
- 5. Biopsy of single quadrant disease (to confirm CIN2)
- 6. Up to 4 further f/u visits follow the same format with the notable exception of the absence of a further biopsy until the 12-month final visit

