4. INTERVENTIONS

1 baseline and up to 4 further colposcopic examinations during the course of the year. This is 1-2 additional follow-up examinations in comparison to the normal 6 monthly follow-up appointments for patients that are currently having conservative management for CIN2

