6.2 Analysis of Endpoints

Each patient will have their samples probed for evidence of lesions. During the follow-up period we will be observing if these lesions progress or regress with concurrent marker pattern changes i.e. if lesion is of low progression potential, we expect high E4 expression and low p16/MCM expression and vice versa. The final endpoint analysis will look for correlation of these biomarker patterns to the final histology or colposcopy outcome. We expect high E4 expression lesions to regress and vice versa.

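### Sections 4.5 and 6.1 disagree on whether women who stop before month 12 count, and Section 6.2 does not say how women treated early enter the analysis

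*Protocol*

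**What the plan says.** **Early action on the marker.** In the Background and Rationale, "any marker pattern that is suggestive of higher-grade disease will result in the patient having a colposcopic visit", followed by counselling and by biopsy or treatment where needed.

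**Who counts.** Section 4.5: "Evaluability is determined by having at least 3 full datasets (3 different time points". Recruitment stops at 10 such women or at the end of 2022, and all data capture stops at the end of 2022 even if 10 has not been reached. Women recruited after the tenth evaluable one "who are still active in the study will be followed -up and included in the final analysis". Section 6.1 mentions drop-out and withdrawn consent, then states "we will only count patients that have completed the full study duration". The protocol does not define full study duration. The Synopsis gives follow-up as 6 months to 1 year.

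**Schedule.** Section 4 (Interventions) plans "1 baseline and up to 4 further colposcopic examinations during the course of the year". Women from the existing clinical pathway join later: "participants will start the study at either the 3 month visit (-/+ 2 week) or the 6 month routine clinical visit". Section 3.4 item 6 describes the follow-up visits with "the notable exception of the absence of a further biopsy until the 12-month final visit".

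**Analysis.** Section 6.2: "The final endpoint analysis will look for correlation of these biomarker patterns to the final histology or colposcopy outcome".

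**The concern.** Two sections fix two different tests for the same group of 10. Section 4.5 counts datasets; Section 6.1 requires completion. They can differ only for women who stop early, and the protocol itself creates one route to stopping early that depends on the marker: treatment after a patch that suggests higher-grade disease.

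Section 6.1 is justified by ordinary drop-out, but its wording also covers a woman whose follow-up ends because she was treated. The only endpoint is the link between marker pattern and progression or regression. Removing women because of their marker result would therefore remove some of the most informative cases from a study of about 10.

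A related gap concerns women treated early who stay under follow-up. Section 6.2 refers to the final outcome. For a woman whose lesion was excised, that could be read as her state after treatment, which reflects the excision rather than the course of the lesion.

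**Working it through.** The sample size of 10 is given without a calculation, so there is no figure to reproduce. The check lists every way of leaving early on the stated schedule.

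**Inputs**
- Patches at months 0, 3, 6, 9 and 12 after diagnosis (Synopsis).
- Entry at month 0, 3 or 6 (Synopsis).
- Section 4.5 test: at least 3 datasets.
- Section 6.1 test: reached month 12, taking the final visit named in Section 3.4 as the full duration. This is a reading, not a stated definition.

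**Step 1: completers.** Datasets = (12 − entry month)/3 + 1, which gives 5, 4 and 3 for entry at month 0, 3 and 6. All completers meet both tests, so any conflict concerns early stoppers only.

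**Step 2: early exits.** For an exit after the scheduled patch at month t < 12, with no further patch, datasets = (t − entry month)/3 + 1.

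| Entry | Last patch (month) | Datasets | 4.5 | 6.1 |
|---|---|---|---|---|
| 0 | 0 | 1 | no | no |
| 0 | 3 | 2 | no | no |
| 0 | 6 | 3 | yes | no |
| 0 | 9 | 4 | yes | no |
| 3 | 3 | 1 | no | no |
| 3 | 6 | 2 | no | no |
| 3 | 9 | 3 | yes | no |
| 6 | 6 | 1 | no | no |
| 6 | 9 | 2 | no | no |

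Of 9 exit points, 3 meet 4.5 but not 6.1, 6 meet neither, and none meets 6.1.

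**Step 3: other ways of counting.** The protocol does not say whether a patch is taken at a triggered visit.
- If one is taken and gives a full dataset, each count rises by 1. Then 6 of 9 meet 4.5 but not 6.1, and 3 of 9 meet neither.
- If the signal is acted on at the next scheduled visit, with its patch, the three exits straight after the entry patch disappear. Of the remaining 6, 3 meet 4.5 only and 3 meet neither.

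**Step 4: six-month reading of 6.1.** Suppose full duration means the Synopsis minimum of 6 months, so t − entry month ≥ 6. In the table above this holds for entry 0 with last patch at 6 or 9, and for entry 3 with last patch at 9. These are the same 3 exits that meet 4.5. On this reading the two rules agree, and the other 6 of 9 still meet neither.

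**Step 5: calendar.** The protocol version is dated 21/01/2022 and data capture ends with 2022. A woman entering at diagnosis after the version date would reach month 12 after 21/01/2023, which is too late. Counting back from the end of 2022, entry by the end of March 2022 still allows the month-9 patch (4 datasets), and entry by the end of June 2022 allows the month-6 patch (3 datasets). Such women are evaluable under 4.5 and, on the month-12 reading, not counted under 6.1, whether or not any marker signal occurs.

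**Step 6: biopsy timing.** The Background and Rationale allows biopsy or treatment when the marker suggests higher-grade disease. Section 3.4 item 6 states no biopsy before the 12-month visit and gives no exception. The two do not agree as written.

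**The case against.** The strongest reply is that the readable text never says a triggered biopsy or treatment ends participation. A woman who is only biopsied can continue to month 12 and meet both rules. Withdrawal points are mentioned in the caption of Fig 3, and the figure is not available here. This stands, so not every woman biopsied or treated early can be called an exit.

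Second, the Section 6.1 sentence sits under the number of participants and follows a remark about drop-out. It may concern only the target of 10. Section 6.2 itself has no completer restriction, and the 4.5 sentence on later recruits adds women without excluding any. This also stands as a possible reading. Even so, the two sections disagree on who makes up the 10.

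Third, a reader might infer that most early exits meet neither rule. That is true only if no patch is taken at the triggered visit and exits straight after entry are counted. Step 3 gives a third or a half otherwise, and in any case these are possible exit points, not probabilities.

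Fourth, a reader might infer that the marker determines its own reference outcome. It can affect when histology is obtained. However, every woman has colposcopy every three months, and the one-year visit includes biopsy or excision, so verification is not reserved for marker-positive women who stay.

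**Conclusion.** The point holds as a minor inconsistency. On the month-12 reading, Sections 4.5 and 6.1 give different answers for 3 of 9 possible early exits (6 of 9 with a patch at the triggered visit). Up to 6 of 9 exits meet neither rule. On the six-month reading the two rules agree. The calendar limit makes the conflict practical for women entering at diagnosis after the version date, even if no marker signal ever occurs.

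Marker-related loss from the 6.2 analysis is conditional. It requires that some women are treated on a marker signal, that their follow-up ends, and that one of the counting rules is used to choose the analysis set. The protocol establishes none of these. The number of such women may be zero, and the size and direction of any bias cannot be derived. A reader might use the quoted regression rate of more than 50% to work out what share of non-regressing women would be lost. That would add the assumption that every woman lost is a non-regressor, which the document does not support.

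The mismatch between Section 3.4 item 6 and the Background and Rationale is separate and needs only a clarifying clause.

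**What to change.** Leave the safety pathway as it is.

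1. In Section 6.1, replace the completer rule with the Section 4.5 definition for counting towards 10. State that all women with at least one patch and an outcome enter the Section 6.2 analysis. For a woman treated early, or whose follow-up ends early, the outcome is the histology at that point, not her state after treatment. A woman biopsied but not treated keeps her final outcome, with the early histology shown as well. Adopting the 4.5 definition alone would not be enough, because it would still leave out up to 6 of the 9 exits.
2. Add to Section 3.4 item 6: *except where a marker pattern or colposcopy suggests disease worse than CIN2*.
3. Present Section 6.2 per woman, flagging marker-triggered outcomes and giving the number of patches behind each.

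The cost is a few sentences and one flag on the case report form, with no extra visits or procedures and no delay to safety action. The drawback is that women with 1 or 2 patches contribute only a short marker series, which is why the number of patches should be shown.

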4.4.2 Sample Analysis

For this feasibility study, we envisage that 10 patients will be adequate.

These will be triple stained with a pan E4 antibody to identify areas of virus infection (LSIL), along with p16/MCM to identify cells that are abnormally progressing through the cell cycle (HSIL). Images of the stained cells will be captured using a digital imaging system prior to H+E staining or staining with the Pap stain. The immunostaining and histology images will be compared against the images taken during the colposcopy examination and with the results of the biopsy analysis. For all patients, we will also request sections from the biopsy material in order to better understand how biomarker expression at the epithelial surface (in the cell-lifts) relates to expression of the same biomarkers in the underlying disease and Patch approach.

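### Adverse marker results return to the colposcopy clinic, whose outcome section 6.2 then correlates with the markers; masking of the histology review is not stated

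*Protocol*

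**What the plan says.** Section 6.2 gives one endpoint analysis: "The final endpoint analysis will look for correlation of these biomarker patterns to the final histology or colposcopy outcome". It also states the expected direction: "We expect high E4 expression lesions to regress and vice versa".

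The Background and Rationale sends marker results into care: "any marker pattern that is suggestive of higher-grade disease will result in the patient having a colposcopic visit", with counselling and with biopsies or treatment as required. The same section wants one named colposcopist for each woman where possible, and photographs compared between visits if a different colposcopist is used. At one year the Synopsis plans "either further biopsy or excisional treatment as per colposcopist impression".

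On histology, the Fig 3 caption says that "all histology will be reviewed/compared by histopathologists", without saying what is compared or what information the readers hold. Section 4.4.2 adds that "we will also request sections from the biopsy material in order to better understand how biomarker expression at the epithelial surface" relates to expression in the underlying tissue. The Background describes the marker panel as one that "improves the sensitivity of subjective approaches such as histology/ cytology".

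The text contains no statement on masking, or on the order in which markers and outcomes are read. Fig 3 itself is not reproduced in the text available, so only its caption could be checked.

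**The concern.** A correlation between marker and outcome is informative only if the outcome is set without knowledge of the marker. Here the clinic that acts on an adverse marker pattern is also the clinic whose impression section 6.2 accepts as an outcome. Because the same colposcopist is preferred throughout, the person who counsels a woman about an adverse pattern is likely to be the one who later judges whether her lesion has progressed or regressed.

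Using the same colposcopist and comparing photographs both address variability between observers. Neither addresses knowledge of the marker.

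With about 10 women, one or two influenced calls can change the message. The pilot could then report a regression or progression pattern that comes partly from its own feedback rule. Section 4.2 makes demonstrating such patterns the primary measure, so this touches the main result.

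**Working it through.** The protocol gives no alpha, power, effect size or concordance threshold, so there is no figure of its own to reproduce. The check has two parts: who can know the marker, and how much that could matter at n = 10.

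**1. Who can know the marker when the outcome is set**

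- *Colposcopist, later visits.* The Background rule brings the woman to a colposcopic visit, with counselling, because of her marker pattern. The clinic can hardly do this without knowing the reason. Any later colposcopy outcome for her can be given with that knowledge.
- *Colposcopist, same visit.* Section 3.4 has the patch lifted (step 3) before the rest of the examination (step 4). The Background says that the disc is probed in the lab. That visit's impression would normally exist before that visit's patch is stained.
- *Histopathologists.* Section 4.4.2 states a separate purpose for the tissue sections, which is to compare surface with underlying expression. No text says that the pathologists receive patch results or stained sections before grading, and none says that they do not.

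**2. Size, as an illustration**

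Input from the protocol: n = 10 (section 6.1). Assumptions not in the protocol:

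- The marker is uninformative, so agreement is 50%.
- 5 of 10 women have an adverse pattern.
- A share q of those women's outcomes is settled in line with the marker.
- At least 8 of 10 concordant is used as a yardstick.

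For an affected woman, p = 0.5 + 0.5q. For the others, agreement stays at 0.5. Expected agreement = (5p + 5 × 0.5)/10.

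Let A be the number concordant among the 5 affected women, A ~ Bin(5, p), and B the number among the other 5, B ~ Bin(5, 0.5). Then

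P(A + B ≥ 8) = P(A=3) × 1/32 + P(A=4) × 6/32 + P(A=5) × 16/32.

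| q | p | Expected agreement | P(A=3), P(A=4), P(A=5) | P(at least 8 of 10) |
|---|---|---|---|---|
| 0 | 0.50 | 50% | 0.3125, 0.1563, 0.0313 | 5.5% |
| 0.20 | 0.60 | 55% | 0.3456, 0.2592, 0.0778 | 0.0108 + 0.0486 + 0.0389 = 9.8% |
| 0.30 | 0.65 | 57.5% | 0.3364, 0.3124, 0.1160 | 0.0105 + 0.0586 + 0.0580 = 12.7% |
| 0.40 | 0.70 | 60% | 0.3087, 0.3602, 0.1681 | 0.0096 + 0.0675 + 0.0840 = 16.1% |

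*Fewer adverse patterns.* With 3 of 10 women affected, the same calculation gives 7.8, 9.2 and 10.7%.

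*Upper case.* If outcomes were steered in all 10 women, X ~ Bin(10, p) gives P(X ≥ 8) = 16.7, 26.2 and 38.3%.

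**3. One woman's influence**

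Take 5 adverse and 5 favourable patterns, with 3 of 5 and 2 of 5 women respectively called non-regressing. Agreement is 6 of 10 and phi = (3×3 − 2×2)/√(5×5×5×5) = 0.20. Re-call one discordant woman in the adverse group and the split is 4 of 5 against 2 of 5. Agreement is then 7 of 10 and phi = (4×3 − 1×2)/√(5×5×6×4) = 0.41.

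**The case against.** The strongest objection is that much of the possible exposure is not documented.

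- *Histopathologists.* A reader might infer from the Fig 3 caption, the tissue staining in section 4.4.2 and the Background remark on subjective histology that pathologists will grade with the markers in view. The documents do not support that. The caption is silent, section 4.4.2 gives the sections another purpose, and the remark describes earlier work on the panel. What stands is only that masking is not stated.
- *Same-visit exposure.* A reader might suppose that the colposcopist knows each visit's patch result. The order of procedures makes this unlikely. Carry-over from an earlier patch remains.
- *Month-12 specimen.* Biopsy and excision both yield tissue, so the colposcopist's choice selects the type of specimen and does not set its grade. This stands.
- *Magnitude.* Steering in all women does not match the one documented channel, which releases only patterns suggestive of higher-grade disease. The all-women figures are therefore an upper case.
- *Pilot status.* This is a 10-woman feasibility study with no formal test or success threshold, which tempers the severity. It does not remove the point, because demonstrating marker patterns is the stated primary measure.

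Leaving the matter to an analysis plan would not be enough. What an assessor knows when grading is a matter of study conduct, and analysis cannot restore masking afterwards.

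**Conclusion.** The point holds for the colposcopy outcome. By the protocol's own feedback rule, an outcome given after an adverse marker result has been released is not independent of the marker with which section 6.2 correlates it. For the histopathologists the finding is limited to silence, and actual exposure is not shown.

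Under the assumptions above, the chance of an uninformative marker reaching 8 of 10 concordant rises from 5.5% to between 9.8% and 16.1%. The share of outcomes influenced and the number of women with adverse patterns are both assumed. The figures show sensitivity at this sample size and do not estimate the bias in this study. The sponsor should address the point, since a cheap remedy exists within the histology review already planned.

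**What to change.** Leave the safety feedback unchanged and make three changes.

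1. **Fig 3 text and section 4.4.2.** State that the planned histology review grades entry and final specimens from coded, routinely stained slides. Patch results and E4/p16/MCM section staining are withheld until the grade is locked.
2. **Section 6.2, outcome.** Use that masked histology grade as the outcome wherever tissue exists, and the colposcopy outcome only where it does not.
3. **Section 6.2, analysis.** Record for each woman whether an adverse marker result had been released to the colposcopist before her outcome was set. Report the correlation with and without the colposcopy-only outcomes set after such a release. Listing these women without the second analysis would leave the one documented channel unaddressed.

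The cost is protocol wording, slide coding, one recorded item per woman and one additional analysis. No extra reader or patient procedure is needed. The small downside is that marker-stained sections reach the pathologists later.
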